## **5. INVESTIGATIONAL MEDICINAL PRODUCTS**

### **5.1. Description and Handling**

#### **5.1.1. Formulation**

ENTO tablets, 200 mg strength, are available as beige, capsule-shaped film-coated tablets debossed with “GSI” on one side and “9973” on the other side. In addition to the active ingredient, ENTO tablets contain the following inactive ingredients: methanesulfonic acid, hydroxypropyl methylcellulose (hypromellose), mannitol, microcrystalline cellulose, crospovidone, poloxamer 188, silicon dioxide, magnesium stearate, polyethylene glycol, polyvinyl alcohol, talc, titanium dioxide, ferrosoferric oxide/black iron oxide, iron oxide red, and iron oxide yellow.

Daunorubicin is administered by IV infusion or IV bolus during Group B induction therapy and is supplied in vials of 20 mg. Each vial contains a red freeze-dried powder of 20 mg (titer) daunorubicin hydrochloride and 100 mg D-mannitol. .

Cytarabine is administered by IV infusion during Group B induction and post-remission chemotherapy. For induction therapy, cytarabine may be supplied in vials of 20 mg, 40 mg, 60 mg, 100 mg or 200 mg solution for injection or concentrate solution for infusion. The pharmacy manual should be referenced for information on the actual vial sizes that will be supplied. If the 100 mg vials are supplied, each vial will contain a 5 ml solution for injection with a concentrate for solution for infusion containing 100 mg cytarabine (20 mg/ml). Each 100 mg vial will also contain a sodium-S-lactate solution (50%), sodium chloride, and water for injections. For post-remission therapy, cytarabine is supplied in vials of 1 g solution for infusion with 20 mL solution that contains 1000 mg cytarabine (50 mg/mL). Each 1 g vial contains sodium-S-lactate solution (50%) and water for injections as a clear, colorless to yellowish solution free of particles.

#### **5.1.2. Packaging and Labeling**

Study drug (ENTO [GS-9973] 200 mg tablets) is packaged in white, high-density polyethylene (HDPE) bottles. Each bottle contains 60 tablets, a silica gel desiccant and polyester packing material. Each bottle is enclosed with a white, continuous thread, child-resistant, polypropylene screw cap fitted with an induction-sealed, aluminum-faced liner.

Gilead will supply daunorubicin and/or cytarabine to each site as study drug and details regarding the packaging and labeling will be provided separately in the pharmacy manual.

Study drugs to be distributed to centers in Japan shall be labeled to meet applicable requirements of the Pharmaceuticals and Medical Devices Agency (PMDA) and/or other local regulations.

### **5.1.3. Storage and Handling**

Study drug (ENTO) should be stored at controlled room temperature of 25°C (77°F); excursions are permitted between 15°C and 30°C (59°F and 86°F). Storage conditions are specified on the label. Until dispensed to the subjects, all bottles of study drugs should be stored in a securely locked area, accessible only to authorized site personnel. To ensure the stability and proper identification, study drug should not be stored in a container other than the container in which they were supplied. Keep the bottle tightly closed to protect from moisture. Consideration should be given to handling, preparation, and disposal through measures that minimize drug contact with the body. Appropriate precautions should be followed to avoid direct eye contact or exposure through inhalation when handling.

Daunorubicin and cytarabine will be supplied as study drug and the site should handle and store them in accordance with the pharmacy manual.

### **5.2. Premedication**

No specific premedications or supporting medications are required in conjunction with ENTO administration. All subjects should receive anti-microbial, anti-fungal, and anti-viral prophylaxis per institutional guidelines.

For cytarabine and daunorubicin, the site should reference the pharmacy manual.

### **5.3. Dosage and Administration**

#### **5.3.1. Entospletinib**

ENTO should be taken under fasted conditions. Fasting is defined as no food or liquids other than water for 2 hours pre- and 1 hour post-dose. Subjects should be instructed not to bite or chew the tablets. In case of breakage of the tablets in the oral cavity, additional water should be taken as a rinse. If a subject is unable to take the whole pill, contact the Sponsor and Medical Monitor for further instructions. Subjects should also be instructed to contact the site staff or investigators if the incorrect dose of ENTO is taken.

ENTO will be administered orally (PO) BID approximately every 12 hours while in a fasted state. Ideally, ENTO should be taken at approximately the same times each day. While it is realized that variations in the dosing schedule may occur, the prescribed regimen should be followed as closely as possible. Compliance with the protocol dosing schedule will be documented in the subject's chart and the electronic data capture (EDC) at each scheduled visit. Counseling regarding subject compliance may be required.

Subjects who have a delay in administration of a dose of ENTO of < 6 hours should take the planned dose as soon as possible after the intended time of administration. For subjects who have a delay in administration of ENTO of ≥ 6 hours, the dose should not be taken. ENTO administration may continue but the missed dose should not be made up and the planned timing of subsequent ENTO dosing should not be altered.

Vomited doses should be retaken, but only if the tablets are visible in the vomitus.

#### 5.3.1.1. Guidelines for ENTO Dose Modifications

Recommendations for dose modifications based on the type and severity of AEs or laboratory abnormalities are provided in [Table 5-1](#). The dose adjustment recommendations are based on the CTCAE grade of specific toxicities. However, exceptions are expected for subjects who initiate study treatment with low blood counts. Clinical judgement should apply, and in cases of uncertainty, the study medical monitor should be contacted.

The dose modification instructions focus on the types of events most commonly attributed to ENTO or other drugs that target B-cell receptor signaling pathways. The recommendations provided in [Table 5-1](#) comprise only guidelines; variations from these recommendations may be warranted based on an investigator's individual judgement in considering potential risks, benefits, and therapeutic alternatives available to each subject.

**Table 5-1. ENTO Dose Modification Guidelines**

Adverse Event	Grade 1	Grade 2	Grade 3	Grade 4
Neutropenia	Maintain current dose level and schedule.			Continue dosing at same or lower dose level at investigator discretion.
Thrombocytopenia	Maintain current dose level and schedule.			Continue dosing at same or lower dose level at investigator discretion.
Dermatological	Maintain current dose level and schedule.		Withhold dosing until $\leq$ Grade 1. Resume dosing at current dose level.	Withhold dosing until Grade $\leq$ 1.
			If re-challenge at current dose level results in recurrence, may resume dosing at same or lower dose level at investigator discretion.	May resume at lower dose level or discontinue dosing at investigator discretion
Hepatic (elevations in ALT, AST, or bilirubin)  Note: If subject has febrile neutropenia, rule out infectious cholecystitis and other infectious causes.	(ALT/AST $\leq$ 3xULN) (Direct Bilirubin $\leq$ 1.5xULN)	(ALT/AST $>$ 3-5xULN) (Direct Bilirubin $>$ 1.5- $\leq$ 3xULN)	(ALT/AST $>$ 5-20xULN) (Direct Bilirubin $>$ 3-10xULN)	(ALT/AST $>$ 20xULN) (Direct Bilirubin $>$ 10xULN)
	Maintain current dose level and schedule.	Maintain current dose level and schedule. Monitor ALT, AST, ALP, and direct bilirubin at least 1x per week.	Withhold dosing. Monitor ALT, AST, ALP, and direct bilirubin at least 1x per week until all abnormalities are Grade $\leq$ 1.	Withhold dosing. Monitor ALT, AST, ALP, and direct bilirubin at least 1x per week until all abnormalities are Grade $\leq$ 1.
			If direct bilirubin was Grade $<$ 3, resume dosing at same dose level. If direct bilirubin was Grade $\geq$ 3, resume at lower dose level.	If direct bilirubin was Grade $<$ 4, resume dosing at lower dose level. If direct bilirubin was Grade 4, discontinue dosing.
Pneumonitis (dyspnea, cough, hypoxia and/or diffuse interstitial pattern or ground-glass opacities on chest CT and no obvious infectious cause) Note: If subject has febrile neutropenia, rule out bacterial /fungal pneumonia.	Maintain current dose level and schedule.	Withhold dosing until Grade $\leq$ 1.  May resume at initial or lower dose level at investigator discretion.	Withhold dosing until Grade $\leq$ 1.  May resume at lower dose level or discontinue dosing at investigator discretion.	
Other Study Drug Related, Non-hematological AEs	Maintain current dose level and schedule		Withhold dosing until Grade $\leq$ 1.  May resume dosing at initial or lower dose level or discontinue dosing at investigator discretion.	

### **5.3.2. Cytarabine and Daunorubicin**

During induction chemotherapy, IV cytarabine 100 mg/m^2 will be administered on Days 1-7 of each cycle. During post-remission chemotherapy, age-adjusted HiDAC will be administered. Subjects ≤ 60 years of age will receive 3 g/m^2 HiDAC BID on Days 1, 3, and 5 of each cycle and subjects > 60 years of age will receive 1 g/m^2 HiDAC once daily on Days 1 to 5 of each cycle.

IV daunorubicin 60 mg/m^2 will be administered on Days 1-3 of each cycle of induction chemotherapy.

The site should administer cytarabine and daunorubicin in accordance with the pharmacy manual.

### **5.4. Prior and Concomitant Medications**

Subjects should receive full supportive care including transfusions of blood and blood products, antibiotics, antiemetics, antifungals, allopurinol, etc., when appropriate.

Nausea and/or vomiting should be treated with maximal medical therapy, which should include a 5HT3 receptor antagonist, unless otherwise contraindicated.

Strong consideration should be given to transfusing subjects with markedly compromised hemoglobin levels (< 8 g/dL) unless contraindicated.

The use of myeloid growth factors during induction chemotherapy is not permitted but during post-remission chemotherapy may be used per guidelines for use in AML. During the DLT assessment period, primary prophylaxis with granulocyte-colony stimulating factor (G-CSF) is not permitted.

### **5.5. Excluded Medication**

During the course of the clinical trial, study subjects are anticipated to continue the use of prescribed medications identified during the screening procedures, consistent with study inclusion and exclusion criteria.

Subjects who initiate therapy with excluded medications will be discontinued from the trial. The following therapies are not permitted at any point during the trial beginning with the first dose of study treatment.

- rEPO is not permitted at any time on the study.
- No other direct anti-leukemia therapy is permitted.
- Palliative radiation therapy may not be administered while the subject is on study.
- Any non-study leukemia directed therapy or non-study leukemia directed immunotherapy (approved or investigational), except steroids used as anti-emetics. Prophylaxis with intrathecal chemotherapy will not be considered as leukemia directed therapy.

- Proton Pump Inhibitors since they are likely to decrease exposure to ENTO. Use of a proton pump inhibitor should be avoided for 7 days prior to study drug administration.  
 Note: H2 blockers and antacids will be allowed for use during the protocol
- Co-administration of strong CYP3A and CYP2C9 inducers, and moderate CYP2C9 inducers are contraindicated in this study. Administration of these medications should be avoided for 2 weeks prior to study drug administration. Examples of these medicines are provided in [Table 5-2](#).

Caution should be exercised when co-administering drugs that are moderate or strong inhibitors of CYP2C9 (eg, fluconazole, voriconazole or amiodarone) as they may increase ENTO exposure.

Caution should be exercised when co-administering medications that are transported by UGT1A1, OATP1B1, OATP1B3, MATE1, P-gp and BCRP; dose adjustment or switching to an alternative medication may be necessary if clinically indicated.

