### **3.5. Discontinuation Criteria**

#### **3.5.1. Discontinuation of Study Treatment**

Study treatment may be discontinued in the following instances:

- Intercurrent illness that would, in the judgment of the investigator, affect assessments of clinical status to a significant degree. Following resolution of intercurrent illness, the subject may resume study dosing at the discretion of the investigator.
- Unacceptable toxicity, or toxicity that, in the judgment of the investigator, compromises the ability to continue study-specific procedures or is considered to not be in the subject's best interest
- Group A: If there is disease progression or if there has not been an improvement in cytopenias, blast count, peripheral blood or marrow that would suggest clinical benefit, the subject should be removed from study treatment per Investigator discretion. Decisions regarding continuation of ENTO monotherapy in subjects should be determined by the Investigator.
- Group A: Requires continued treatment with hydroxyurea after Cycle 1
- Group B: If a CR or CRi is not achieved by the end of induction Cycle 2, the subject will be considered to have refractory leukemia, to meet the definition of treatment failure and study endpoint criteria, and will be discontinued from the study treatment

- Subjects may be removed in the case of new CNS disease or other new sites of extramedullary involvement
- Subject request to discontinue for any reason. Subjects who withdraw from the study treatment phase of the study should still be followed for survival until 3 years from the last study visit (see Section 6.8.3, Long term follow up)
- Subjects with noncompliance to study treatment administration, study procedures, or study requirements that increase risk or substantially compromise the interpretation of study results should be withdrawn from study treatment.
- Pregnancy or breastfeeding begins during the study
- The investigator, in consultation with the Gilead Sciences Medical Monitor or designee, may withdraw any subject from the study treatment, if, in the investigator's opinion, it is not in the subject's best interest to continue.
- Initiation of non-study specific anti-cancer therapy
- Discontinuation of the study treatment at the request of Gilead, a regulatory agency or an institutional review board or independent ethics committee (IRB/IEC)

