### **3.6. End of Treatment**

Subjects will be removed from study treatment when any of the criteria listed in Section 3.5.1 apply. The End of Treatment (EOT) visit should be completed when a subject discontinues study treatment and prior to initiating a new therapy.

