**Table 5-2. Contraindicated Medications in this Study that require prior MM discussion and approval**

	Strong	Moderate
CYP3A Inducer	carbamazepine, phenytoin, rifampin, St. John's Wort, enzalutamide, rifabutin, phenobarbital, mitotane, *avasimibe	Not prohibited
CYP2C9 Inducer		carbamazepine, rifampin, *ritonavir, enzalutamide
Proton Pump Inhibitors	omeprazole, esomeprazole, *pantoprazole, lansoprazole, rabeprazole, *dexlansoprazole, vonoprazan	

\* Not yet approved in Japan

In a study in healthy volunteers, ENTO 400 mg BID increased rosuvastatin exposure by approximately 3.8-fold, which may theoretically increase the risk of AEs. The following restrictions apply to the use of HMG-CoA reductase inhibitors with ENTO:

HMG-CoA reductase inhibitor	Dose Adjustment Required
Atorvastatin	Maximum dose 20 mg QD
Rosuvastatin	Maximum dose 10 mg QD
Pravastatin	Maximum dose 40 mg QD
Simvastatin	Maximum dose 20 mg QD
*Lovastatin	Maximum dose 20 mg QD
Fluvastatin	Maximum dose 20 mg BID or 40 mg QD
Pitavastatin	Maximum dose 1 mg QD

\* Not yet approved in Japan

The management of subjects who are benefiting from the protocol treatment and who subsequently require treatment with the above medications should be discussed with the Medical Monitor.

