## **6.6. Assessments for Premature Discontinuation from Study**

If a subject prematurely discontinues study treatment (see Section 3.5.1, Discontinuation of Study Treatment), every attempt should be made to keep the subject in the study and continue to perform the required study-related follow-up and procedures (see Sections 6.8). If this is not possible or acceptable to the subject or investigator, the subject may be withdrawn from the study and no further study-related follow-up and procedures will be performed.

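### Protocol 5.5 discontinues subjects who start an excluded medication from the trial, whereas 3.5.1, 6.6 and 6.8.3 stop study treatment and keep follow-up going (minor)

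*Protocol*

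**What the plan says.** Section 5.5 sets the consequence of starting a prohibited drug: "Subjects who initiate therapy with excluded medications will be discontinued from the trial". The prohibition runs from the first dose through the whole trial. The list covers rEPO, palliative radiation, proton pump inhibitors, certain CYP inducers and other leukemia treatment ("No other direct anti-leukemia therapy is permitted").

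The same section then gives Table 5-2, which names the proton pump inhibitors and CYP inducers. Its title is "Contraindicated Medications in this Study that require prior MM discussion and approval". After a further table of statin dose limits, the section closes by saying that management of benefiting subjects "who subsequently require treatment with the above medications should be discussed with the Medical Monitor".

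Elsewhere the protocol separates stopping treatment from leaving the study:

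- Section 3.5.1 opens with "Study treatment may be discontinued in the following instances" and includes "Initiation of non-study specific anti-cancer therapy".
- Section 3.5.2, the list of reasons for leaving the study, names neither excluded medication nor new anti-cancer therapy.
- Section 3.6 places the End of Treatment visit "when a subject discontinues study treatment and prior to initiating a new therapy".
- Section 6.6 says that after premature discontinuation of treatment "every attempt should be made to keep the subject in the study".
- Section 6.8.3 then provides six-monthly contacts, for at most 3 years, to record leukemia treatments, other malignancies and survival.

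**The concern.** The consequence in Section 5.5 is attached to the wrong level. For a subject who starts another leukemia therapy, the rest of the protocol has a clear sequence: stop ENTO, hold the End of Treatment visit, start the new therapy, enter long-term follow-up. Section 5.5 instead takes that subject out of the trial.

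This is a stated rule that gives a worse result if it is obeyed. A site that follows Section 5.5 would stop recording survival and subsequent treatment at the change of therapy. A site that follows Sections 6.6 and 6.8.3 would continue. Both could say that they had followed the protocol.

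**Working it through.** The protocol gives no figure to reproduce. The check is a comparison of text, followed by a bound on what could be lost.

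**Step 1: which level each section acts on, for a subject starting new leukemia therapy.**

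| Section | What happens | Level |
|---|---|---|
| 5.5 | Mandatory discontinuation | Trial |
| 3.4 | Start of new therapy ends ENTO | Study treatment |
| 3.5.1 | New anti-cancer therapy is a listed reason to stop | Study treatment |
| 3.5.2 | Not listed | Study |
| 6.6 | Retention sought after treatment stops | Study continues |
| 6.8.3 | Later leukemia treatments and survival collected | Study continues |

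Section 5.5 is the only one of these that ends trial participation.

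**Step 2: can Section 5.5 be read literally?** Its prohibition lasts for the whole trial. If *trial* includes long-term follow-up, any subject who receives a leukemia treatment during follow-up must be removed. The leukemia-treatment item in Section 6.8.3 could then not be collected as intended. The sections fit together only if *trial* in Section 5.5 means study treatment.

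**Step 3: the Medical Monitor route.** The exemptions inside the Section 5.5 list (anti-emetic steroids, intrathecal prophylaxis, H2 blockers, antacids) define what is not excluded. They do not soften the consequence. The title of Table 5-2 does soften it, for proton pump inhibitors and CYP inducers, by providing for prior approval. The closing sentence of the section is weaker evidence, because it directly follows the statin table and may refer to statins only. The rule sentence therefore lacks a pointer to a route that exists.

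**Step 4: bound on lost survival contacts.** Inputs from Section 6.8.3: one contact every 6 months, for at most 36 months. Full contacts lost = follow-up otherwise available / 6, rounded down. The follow-up lengths are assumed, because the documents give none.

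| Assumed follow-up (months) | Calculation | Contacts lost |
|---|---|---|
| 3 | 3/6 = 0.5 | 0 |
| 6 | 6/6 | 1 |
| 12 | 12/6 | 2 |
| 24 | 24/6 | 4 |
| 36 | 36/6 | 6 |

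Six is a ceiling. Section 4.2 requires a life expectancy of only 3 months or more, and SAP Section 1 says the study will be terminated early.

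**Step 5: effect on analyses.** Protocol Section 8.5 censors OS at the last date known alive, which for such a subject would lie close to the switch. SAP Section 3 reports 9 enrolled subjects and limits efficacy to listings, so the effect would be at most a shorter survival record in a listing. DLT evaluability depends on 21 days of ENTO within the window, so for a given stopping day it is the same whether the subject leaves treatment or leaves the trial. Adverse event collection under Section 7.3 is tied to 30 days after the last dose, not to trial status.

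**The case against.** The strongest reply is that *trial* is loose wording and that the sections governing follow-up settle the meaning. The protocol does mix these terms. For failure to reach CR/CRi by the end of Cycle 2, Section 3.2.3 speaks of discontinuation from the study, while Sections 3.5.1 and 6.5.2 speak of study treatment. Sections 6.6 and 6.8.3 both press for retention, and a site would have good reason to follow them. This makes actual harm less likely. It does not make the Section 5.5 sentence correct, and it shows a second place with the same slip.

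Three stronger readings are tempting, and the documents do not support them:

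- *Section 5.5 bars a benefiting subject from any Medical Monitor exception.* A reader might infer this from the sentence alone. The title of Table 5-2 largely answers it: Section 5.5 can be read as the default and the table as the approval route.
- *Section 6.6 confirms that such a subject has no further follow-up.* The clause ending follow-up applies only where retention is not possible, or not acceptable to the subject or the investigator. Starting an excluded drug is not in itself such a case.
- *Section 3.5.2 rules out this reason for leaving the study.* Its list is not stated to be exhaustive, so its silence is only weak support.

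It is also fair to say that the loss is hypothetical. The contact counts are schedule arithmetic, and the SAP's exploratory efficacy sections are redacted, so the presence of an OS listing cannot be confirmed.

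**Conclusion.** The inconsistency is real and limited. Section 5.5 prescribes leaving the trial for an event that Section 3.5.1 handles by stopping treatment, and for which Sections 6.6 and 6.8.3 provide continued follow-up. Obeyed literally, it would end survival follow-up at the switch of therapy. The Medical Monitor element is no more than a missing cross-reference.

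Severity is minor and action optional. The range is 0 to 6 lost contacts per affected subject, on assumed follow-up of 3 to 36 months. Group A is fully enrolled and Group B will not open, so the wording now reaches only subjects still on treatment or in follow-up. A reader might infer that OS estimates or DLT conclusions are compromised. The documents do not show this: efficacy is listed for 9 subjects, and no DLT or primary analysis is shown to change.

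**What to change.** Reword the Section 5.5 sentence along these lines: *Subjects who initiate an excluded medication will be discontinued from study treatment (not from the study), unless, for a Table 5-2 medication, the Medical Monitor has given prior approval; safety and survival follow-up continue per Sections 6.6 and 6.8.*

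In Section 3.2.3, change the outcome for no CR/CRi by the end of Cycle 2 to discontinuation from study treatment, matching Sections 3.5.1 and 6.5.2. With Group B not opening, this is for consistency only.

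No new item is needed in Section 3.5.1. A mandatory item there would sit under a permissive lead-in and create a fresh mismatch.

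The cost is two edited sentences, with no change to data collection, analysis or programming. They are still a protocol modification, which under Sections 9.1.2 and 9.2.1 must be submitted to the ethics committee and approved before use. In a study that is closing, that may be a reason to leave the text as it is.
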